### 10. STUDY CALENDAR

Parameter	Pre TX	CBI Cycle#1, Day 1	SBRT 4-5 Fx~	CBI Cycle#2, Day 1	CBI Cycle#3, Day 1	CBI Cycle #4, Day 1	CBI Cycle #5, Day 1	CBI Cycle #6, Day 1	FU% 1 mo $\Sigma$	FU% 6wks $\Sigma$	FU% 2mo $\Sigma$	FU% 3mo $\Sigma$	FU% 6mo@	FU% 12mo@	FU% 18mo@	FU% 24mo@	FU% 30mo@	FU% 36mo@	
Informed Consent	X																		
Demographics	X																		
Med HX & Medication Rev	X								X		X	X	X	X	X	X	X	X	X
Physical Exam	X				X				X		X	X	X	X	X	X	X	X	X
Standard of Care Labs#	X	X +		X +	X +	X +	X +	X +	X	X	X	X	X	X	X	X	X	X	X
Serum Pregnancy Test	X																		
Urine Pregnancy Test				X		X		X											
Free T4 and TSH	X	X				X			X										
CT or MRI Chest Imaging	X					X $\Sigma$				X			X	X	X	X	X	X	X
CT Abd/Pelvis or PET Scan	X																		
Avelumab Administration ^		X		X	X	X	X	X											
Research Blood Draw	X*				X*														
Recist 1.1 Measurement	X												X	X	X	X	X	X	X
AE Evaluation	X	X	X	X	X	X	X	X	X	X	X	X	X	X	X	X	X	X	X

#: Standard of Care Labs include: CBC and CMP  
 + Prior to each Avelumab dose

@ +/- 10 day  $\Sigma$  +/- 4 days

^ Each cycle of Avelumab is 14 days. Drug is administered on day 1 of each cycle.  
 ~ SBRT: to be administered in 4-5 fractions at the discretion of the treating Radiation Oncologist  
 % Follow-up appointments will be scheduled based on date of SBRT completion. These will begin during Avelumab treatment.  
 \* indicates optional

## 11. MEASUREMENT OF EFFECT

### 11.1 Antitumor Effect-Solid Tumors

For the purposes of this study, patients should be re-evaluated for response 6 months after the initial treatment, 12 months after treatment, and at 6 month intervals thereafter.

Response and progression will be evaluated in this study using the new international criteria proposed by the Response Evaluation Criteria in Solid Tumors (RECIST 1.1) Committee (30). Changes in only the largest diameter (unidimensional measurement) of the tumor lesions are used in the RECIST criteria.

### 11.2 Definitions

Evaluable Population: will consist of all patients who have received 1 cycle of CBI treatment preceding SBRT.

Safety Population: Will consist of all subjects who were enrolled and have received CBI combined with SBRT. This will be used to assess the clinical safety and tolerability of the study.

Evaluable for Objective Response: Only those patients who have measurable disease present at baseline, have completed all fractions of SBRT, and have had their disease re-evaluated will be considered evaluable for response. These patients will have their response classified according to the definitions stated below.

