## **6.3 Therapeutic Procedures**

### **6.3.1 Avelumab Administration**

Each cycle of Avelumab is 14 days. Avelumab is administered on an outpatient basis. Avelumab 10mg/kg body weight, diluted with 0.45% or 0.9% saline solution, will be administered as a 60 minute intravenous (IV) infusion every 2 weeks, on day 1 of each cycle. No Avelumab dose reductions are permitted on this study. Specific instructions for the preparation infusion fluid and administration of infusion solution are provided in the Pharmacy Manual.

After the initial cycle, the patient will receive 5 additional cycles of adjuvant Avelumab per protocol for a total of 6 cycles. Patients will be evaluated for adverse events/toxicities after receiving the first dose of Avelumab.

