### **6.3.2 SBRT Procedures**

Upon enrollment on the protocol patients will be seen by at least one of the Co-Investigator Medical Oncologists. As per standard of care a 4D CT simulation will be performed with fabrication of a radiation therapy immobilization device (such as a Vac-Lok) which will be custom made for each patient. The treating radiation oncologist will identify the location of the tumor. Gross tumor volume (GTV) delineation will be performed on sequential axial computed tomography images. An SBRT treatment plan will be developed based on tumor size and location. The radiation dose will be prescribed using the current clinical practice standard of care of either 12Gy x 4 fractions or 10Gy x 5 fractions at the discretion of the treating radiation oncologist.

Adjacent normal structures including but not limited to the chest wall, spinal cord, lung, airways at risk, vessels at risk, heart, esophagus, aorta, liver, and stomach within 5 cm of the GTV will be identified for the purpose of limiting incidental radiation to these structures.

The patient will receive the first fraction of SBRT within 3-10 days after starting the 1st cycle of Avelumab. SBRT will be administered using image-guidance as per standard of care. An Vac-Lok (or equivalent immobilization device such as Alpha-Cradle) will be used to minimize movement of the chest, spine, and abdomen during treatment. During treatment, cone beam images of the patient's body site of interest will be obtained. Cone beam scan will be obtained immediately prior to treatment and will be repeated until the treatment shift, required to align the Radiation planning scan and the cone beam scan performed on the day of treatment. Cone beam scanning is standard of care for definitive stereotactic body radiation therapy.

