#### 6.7 Criteria for Removal of Subjects from Study Treatment and Study

- Unacceptable adverse events grade IV or greater with an attribution of possibly related while on CBI or after SBRT.
  - Subject withdraws consent for follow-up;
  - Subject is lost to follow-up;
  - Subject dies;
  - Study is terminated for any reason.
- ξ The patient has a confirmed positive serum pregnancy test;

ξ General or specific changes in the patient's condition render the patient unacceptable for further treatment in the judgment of the investigator;

ξ Administrative Decision

Subject can elect to discontinue treatment at any time. If participants withdraw from the study, they will be followed for survival data.

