### B. Management

**Table 1 Treatment Modification for Symptoms of Infusion-Related Reactions**

NCI-CTCAE Grade	Treatment Modification for Study Drug
Grade 1 – mild Mild transient reaction; infusion interruption not indicated; intervention not indicated.	Decrease the study drug infusion rate by 50% and monitor closely for any worsening. The total infusion time for study drug should not exceed 120 minutes.
Grade 2 – moderate Therapy or infusion interruption indicated but responds promptly to symptomatic treatment (for example, antihistamines, NSAIDs, narcotics, IV fluids); prophylactic medications indicated for $\delta$ 24 h.	Stop study drug infusion. Resume infusion at 50% of previous rate once infusion-related reaction has resolved or decreased to at least Grade 1 in severity, and monitor closely for any worsening.
Grade 3 or Grade 4 – severe or life-threatening Grade 3: Prolonged (for example, not rapidly responsive to symptomatic medication and/or brief interruption of infusion); recurrence of symptoms following initial improvement; hospitalization indicated for clinical sequelae. Grade 4: Life-threatening consequences; urgent intervention indicated.	Stop the study drug infusion immediately and disconnect infusion tubing from the subject. Subjects have to be withdrawn immediately from study drug treatment and must not receive any further study drug treatment.

IV = intravenous; NCI-CTCAE = National Cancer Institute-Common Terminology Criteria for Adverse Event; NSAIDs = nonsteroidal anti-inflammatory drugs.

Once the avelumab infusion rate has been decreased by 50% or interrupted due to an infusion-related reaction, it must remain decreased for all subsequent infusions. If the subject has a second infusion-related reaction Grade  $\geq 2$  on the slower infusion rate, the infusion should be stopped and the subject should be removed from study treatment. If a subject experiences a Grade 3 or 4 infusion-related reaction at any time, the subject must discontinue study drug. No Avelumab dose reductions are permitted on this study. Patients who experience grade IV toxicity will continue to be followed until toxicity resolution to Grade  $\leq 1$  or return to baseline.

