## **15. STATISTICAL CONSIDERATIONS**

### **15.1 Endpoints**

#### **15.1.1 Primary Objectives**

Phase I: The Phase I primary endpoint is safety and tolerability as described in Section 3.1.1. Tolerability and safety of will be determined after all patients have completed six doses or have discontinued dosing prior to completing six doses. Safety analyses will be performed in all treated subjects. Descriptive statistics of safety will be presented using National Cancer Institute (NCI) Common Terminology Criteria for Adverse Events (CTCAE) version 4.0.

Phase II: The Phase II primary endpoint is to determine the relapse free survival rate at a median followup of 2 years in early stage NSCLC treated with definitive SBRT combined with 6 cycles of concurrent and adjuvant Avelumab.

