### **15.6 Evaluation of Toxicity**

All patients will be evaluable for toxicity from the time of their first treatment of CBI.

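### The Safety Population in Section 11.2 requires both avelumab and SBRT, which contradicts Sections 15.1.1 and 15.6 and leaves out patients lost to toxicity before SBRT

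*Combined protocol and SAP*

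**What the plan says.** Three places in the combined protocol and SAP say who is counted for safety.

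- Section 11.2 (Definitions), on the Safety Population: "Will consist of all subjects who were enrolled and have received CBI combined with SBRT". The purpose follows: "This will be used to assess the clinical safety and tolerability of the study".
- Section 15.1.1 (Primary Objectives), in the Phase I paragraph: "Safety analyses will be performed in all treated subjects".
- Section 15.6 (Evaluation of Toxicity): "All patients will be evaluable for toxicity from the time of their first treatment of CBI".

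The order of treatment is fixed in Section 6.3.2: "The patient will receive the first fraction of SBRT within 3-10 days after starting the" first avelumab cycle. Toxicity assessment does not wait for radiation. Section 6.3.1 says: "Patients will be evaluated for adverse events/toxicities after receiving the first dose of Avelumab".

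Two provisions can act between the first dose and the first fraction. Section 6.7 lists grounds for removal from study treatment and study. They include death and this criterion: "Unacceptable adverse events grade IV or greater with an attribution of possibly related while on CBI or after SBRT". For grade 3 or 4 infusion reactions, Table 1 in Section 8.2 says: "Subjects have to be withdrawn immediately from study drug treatment and must not receive any further study drug treatment".

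**The concern.** A set that requires receipt of both components depends on what happens after the first dose. Patients who never reach SBRT because of early avelumab toxicity are the ones a safety analysis most needs to keep, and 11.2 removes both the event and the patient. Safety and tolerability is the Phase I primary endpoint, it is judged on 12 patients, and 11.2 is the only place that defines a named safety set. No passage says whether 11.2 or Section 15 governs. Two analysts could therefore report different toxicity rates from the same data, each following the protocol.

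**Working it through.** No design figure in the documents rests on this definition, so there is nothing of the plan's own to reproduce. The check compares the definitions and then illustrates the size.

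**1. Who is counted, definition by definition**

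| Patient | 11.2 | 15.1.1 | 15.6 |
|---|---|---|---|
| Avelumab, then SBRT | in | in | in |
| Avelumab stopped after dose 1, SBRT still given | in | in | in |
| Avelumab given, death or removal before any SBRT | out | in | in |

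The definitions disagree only on the third row. Section 15.6 is the clearest conflict, because it starts evaluability at the first avelumab dose. The wording of 15.1.1 is looser, but its plain meaning also includes a patient treated with avelumab alone.

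**2. Direction of the bias**

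Let x of n patients have the toxicity outcome, and let k of those x stop before SBRT. The rate moves from x/n to (x − k)/(n − k), which is smaller whenever x < n. A patient who misses SBRT for a reason other than toxicity leaves only the denominator, which moves the rate slightly the other way. The downward bias therefore concerns patients lost to toxicity.

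**3. How often an exclusion could occur**

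The documents give no rate of stopping before SBRT. Assume a rate q, independent between patients. The chance of at least one exclusion in n patients is 1 − (1 − q)^n. The sizes are from Section 15.2: 12 in Phase I and 56 in total.

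| Assumed q | n = 12 | n = 56 |
|---|---|---|
| 1% | 1 − 0.99^12 = 11% | 1 − 0.99^56 = 43% |
| 2% | 1 − 0.98^12 = 22% | 1 − 0.98^56 = 68% |
| 5% | 1 − 0.95^12 = 46% | 1 − 0.95^56 = 94% |

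**4. What one exclusion would do if 11.2 were applied to the Phase I rule**

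Section 15.4 calls the combination tolerable if no more than one-third discontinue for related events before six doses, and suspends the study at 4 or more. Take 4 related discontinuations among 12.

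- All dosed patients counted: 4/12 = 33.3%. This is exactly one-third, so it meets the tolerable condition and the suspension trigger together.
- One of the four stopped before SBRT and is excluded: 3/11 = 27.3%, which meets only the tolerable condition.
- Two of the four excluded: 2/10 = 20.0%, with the same result.

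This step is conditional, because 15.3 and 15.4 do not refer to the 11.2 set.

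**The case against.** The best case for leaving the text alone is that Section 15 is where the analysis is specified and it already includes everyone treated, while 11.2 sits under measurement of effect. Early events would also not be lost from view. The study calendar schedules adverse event evaluation from Cycle 1 Day 1, Section 12.5.2 starts SAE reporting at treatment initiation, and under Section 13 the DMC reviews all available data. This stands as far as it goes: collection and oversight are intact. What remains at risk is the reported toxicity summary, because 11.2 claims that task by name. Reading 11.2 as patients assigned to the combination does not rescue it, since its condition is receipt.

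Three stronger readings are tempting, and the documents do not support them.

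- **Every severe infusion reaction at dose 1 leads to exclusion.** Table 1 withdraws study drug and does not mention SBRT. A patient who stops avelumab and then has SBRT has received both and stays in the 11.2 set. Removal from study treatment and study under 6.7 could prevent SBRT, but its toxicity criterion applies at grade IV or greater.
- **The published infusion reaction rate gives the exclusion rate.** Section 4.2 reports 4 infusion reactions of grade 3 or higher among 184 patients, or 2.2%. On that figure the chance of at least one such reaction is 1 − (1 − 4/184)^12 = 23% in 12 patients and 71% in 56. Those patients had advanced disease and were treated every two weeks until progression, confirmed complete response or toxicity. The reactions are not stated to be first-dose events, and none is said to have led to cancelled radiation. The 23% and 71% are chances of a reaction, not of an exclusion.
- **One excluded patient will change the Phase I decision.** The rules in 15.3 and 15.4 count the safety cohort, the subjects and the Phase I cohort. On that wording, a patient who discontinues avelumab for toxicity is counted in 15.4 with or without SBRT.

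**Conclusion.** The contradiction is real and the 11.2 definition is wrong as written for a safety set. If followed, it leaves out patients who die or are removed for toxicity before any SBRT and so understates toxicity. How often this would happen cannot be read from the documents. Over the assumed range of 1% to 5%, at least one exclusion has a chance of 11% to 46% in Phase I and 43% to 94% across 56 patients, and the number excluded may well be small. An effect on the Phase I decision, such as 4/12 read as 3/11, arises only if someone applies the 11.2 set to 15.3 or 15.4. The case for change rests on the conflict and the direction of the bias, which do not depend on the assumed rates.

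**What to change.** - In 11.2, define the Safety Population as all patients who received any dose of avelumab or any fraction of SBRT.
- In 15.1.1 and 15.6, refer to that population by name.
- In 15.3 and 15.4, state that patients who received avelumab but no SBRT are counted.
- If wanted, report the subset that received both components as a supplementary table.

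Two neighbouring points should be reconciled in the same edit. Section 15.3 times the run-in observation from radiation in one sentence and from therapy in another, and the first is undefined for a patient without radiation. In 15.4, 4 of 12 satisfies both the tolerable condition and the suspension trigger.

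The cost is one sentence in 11.2, two cross-references and a clarifying sentence in each of 15.3 and 15.4. Treatment, visits, data collection and sample size do not change.

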### 11.3 Disease Parameters

Measurable Disease: Measurable lesions are defined as those that can be accurately measured in at least one dimension (longest diameter to be recorded) as  $\geq 0.5$  cm with diagnostic techniques (CT, PET/CT (all are optional), or MRI). All tumor measurements must be recorded in centimeters.

## 11.4 Methods for Evaluation of Measurable Disease

All measurements should be taken and recorded in metric notation. All baseline evaluations should be performed as closely as possible to the beginning of treatment and never more than 6 weeks before the beginning of the treatment.

The same method of assessment and the same technique should be used to characterize each identified and reported lesion at baseline and during follow-up. Imaging-based evaluation is preferred to evaluation by clinical examination when both methods have been used to assess the antitumor effect of a treatment.

Conventional CT, PET/CT (all are optional), and MRI These techniques should be performed with cuts of 10 mm or less in slice thickness contiguously. Spiral CT should be performed using a 5 mm contiguous reconstruction algorithm. This applies to tumors of the chest, abdomen, and pelvis.

## 11.5 Response Criteria (via RECIST 1.1)

### 11.5.1 Evaluation of Target Lesions

Complete Response (CR): Disappearance of targeted lesion.

Objective Response (OR): At least a 30% decrease in the sum of the longest diameter (LD) of targeted lesion.

Progressive Disease (PD): At least a 20% increase in the sum of the LD of Targeted lesion.

Stable Disease (SD): Neither sufficient shrinkage to qualify for PR nor sufficient increase to qualify for PD, taking as reference the smallest sum LD since the treatment started

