### 11.5.2 Duration of Response

Response will be defined as evidence of CR, PR, or stable disease. The duration of response will be measured from the start of treatment until the criteria for progression are met.

Duration of CR or PR: The duration of CR or PR will be recorded from the time measurement criteria are met for CR or PR (whichever is first recorded) until the first date that current or progressive disease is objectively documented (taking as reference for progressive disease the smallest measurements recorded since the treatment started).

Duration of Stable Disease: Stable disease is measured from the start of the treatment and must be at least 6 months in duration or until the criteria for progression are met,

taking as reference the smallest measurements recorded since the treatment started.

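### Target progression is written as a 20% increase with no minimum in millimetres, so reading error in a small residual tumour can count as a relapse in the primary endpoint, and the plan does not say whether this text or full RECIST 1.1 governs

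*Combined protocol and SAP*

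**What the plan says.** - **Threshold.** Section 11.5.1 defines progressive disease of the target as "At least a 20% increase in the sum of the LD of Targeted lesion". No absolute increase is required, and this line names no reference value.
- **Reference.** The stable-disease line of 11.5.1 refers to the smallest sum since treatment started. Section 11.5.2 does the same for progression: "taking as reference for progressive disease the smallest measurements recorded since the treatment started".
- **Recording and imaging.** Section 11.3: "All tumor measurements must be recorded in centimeters", with no number of decimals. Section 11.4: "Spiral CT should be performed using a 5 mm contiguous reconstruction algorithm". Neither gives a figure for reading error.
- **Link to the endpoint.** Section 6.4 uses RECIST measurements at 6 months, 1 year and 2 years to determine locoregional control and RFS. Section 11.5.3 counts first documented progression, or death, as the RFS event. The calendar in Section 10 also schedules RECIST measurements at 18, 30 and 36 months.
- **Safeguards.** Section 11.5.4 has a co-investigator radiologist review responses, and 11.4 asks for the same technique throughout. No section requires a confirming scan or biopsy, or gives a rule to separate change after SBRT from relapse.
- **Governing criteria.** Sections 11.1 and 11.5 name RECIST 1.1. They do not say whether the full criteria or the definitions written out here decide a case.

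**The concern.** A purely relative rule becomes more sensitive as the reference shrinks. Stage I tumours of at most 5.0 cm (Section 1) are treated with curative intent, so small residuals are plausible, and with a single target no second lesion dilutes an error in the sum. Because the reference is the lowest reading so far, one low reading lowers the bar for every later one.

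A stable residual misread as growing becomes a permanent RFS event, and it also counts in LRC, TTLP and TTP. The trial has one arm and compares with a fixed 2-year RFS of 80%, so there is no concurrent control in which the same noise would occur. Section 15.2 seeks a 10-point gain (80% to 90%), so a few points of false relapse would use up a material part of it.

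**Working it through.** **1. Growth that triggers progression.** Trigger = 0.20 × smallest diameter so far.

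| Smallest diameter | 5 mm | 10 mm | 15 mm | 20 mm | 25 mm | 50 mm |
|---|---|---|---|---|---|---|
| Growth needed | 1 mm | 2 mm | 3 mm | 4 mm | 5 mm | 10 mm |

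The 1 to 2 mm trigger therefore applies only to residuals of about 5 to 10 mm. The choice of reference matters: against a 25 mm baseline, progression would need 1.2 × 25 = 30 mm, and a stable 10 mm residual would be in no danger.

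**2. Chance of false progression.** The documents give neither residual size nor reading error, so these inputs are assumptions: baseline 25 mm, a residual that is truly constant, and independent normal reading error with SD s of 0.5 to 1.5 mm. An event is a reading at least 20% above the running minimum.

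Hand check for two readings of an unchanged lesion of size L: the second is at least 1.2 times the first with probability 1 − Φ(0.2L / (s√(1 + 1.2²))). For L = 10 and s = 1 this is 1 − Φ(2/1.562) = 1 − Φ(1.28), about 10%. More readings give more chances.

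Simulated false progression by 24 months:

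| Residual | Readings | s = 0.5 | 0.75 | 1.0 | 1.5 mm |
|---|---|---|---|---|---|
| 10 mm | 3 (6, 12, 24 months; Section 6.4) | 1.5% | 11% | 23% | 42% |
| 10 mm | 4 (adds 18 months; calendar) | 2.8% | 19% | 37% | 61% |
| 15 mm | 3 | 0.0% | 1.4% | 7% | 23% |
| 15 mm | 4 | 0.0% | 3% | 13% | 37% |
| 20 mm | 3 | 0.0% | 0.1% | 1.4% | 11% |
| 20 mm | 4 | 0.0% | 0.2% | 3% | 19% |

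**3. The same runs with a 5 mm minimum added.** A 5 mm minimum overrides the 20% rule below 5/0.20 = 25 mm. With four readings, false progression is about 0.1% or less for s up to 1.0 mm and about 5% at 1.5 mm, for all three residual sizes. The protection is not complete: at s = 2 mm, four readings of a 10 mm residual give 72% without the minimum and 17% with it.

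**4. Effect on the primary test.** Section 15.2 states 56 patients after a 10% dropout allowance and 80% power (80% versus 90%, one-sided 0.10). Evaluable: 56 × 0.9 = 50.4, about 50. That 80% was not reproduced at 50 evaluable: a normal approximation gives 74.2%. An exact binomial test needs 45 or more event-free (α = 4.8%, power 61.6%), since 44 or more gives α = 10.3%. That mismatch is a separate matter; the exact test is used here only to size the consequence.

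If a share f of truly event-free patients is wrongly called progressed, a true 90% is observed as 0.90 × (1 − f):

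| f | Observed when truth is 90% | Power (45 or more of 50) | Rejection when truth is 80% |
|---|---|---|---|
| 0% | 90.0% | 61.6% | 4.8% |
| 2% | 88.2% | 45.3% | 2.7% |
| 5% | 85.5% | 24.9% | 1.1% |
| 10% | 81.0% | 6.7% | 0.2% |

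At f = 11.1% a true 90% is observed as 80%. Power falls with f, and so does the type I error.

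**5. From residuals to f.** f = (share of event-free patients with such a residual) × (false rate in step 2). If, as an assumption, 10% had a 10 mm residual and s = 1.0 mm with three readings, f = 0.10 × 23% = 2.3%. For f to reach 11.1% from this source alone, 11.1/23 = 48% of patients would need such a residual.

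**The case against.** The strongest reply is that RECIST 1.1 is named in 6.4, the calendar, 11.1 and the heading of 11.5, so 11.5.1 is shorthand and the full criteria decide. That reading is open. The documents do not reproduce those criteria or give them precedence, and a site working from 11.5.1 would apply a bare 20%. This limits the point to what happens if the written rule is applied. A reader might go further and infer that the plan contradicts RECIST 1.1; that cannot be shown from the documents.

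Second, the size rests on assumptions. This stands. At a reading SD of 0.5 mm a 10 mm residual gives only 1.5 to 2.8%, and a 20 mm residual practically none. Radiologist review and consistent technique may also remove some errors, although neither is a decision rule. The progression rule behind the historical 80% is not described either; an equally noisy rule there would offset part of the bias.

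Third, the rule errs on the cautious side. This is correct: it makes a false claim of benefit less likely, and the harm is a missed effect.

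Two further inferences are tempting and do not hold:

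- The 0.5 cm limit in 11.3 ("Measurable lesions are defined as those that can be accurately measured in at least one dimension") is not the cause. With 11.2 it decides who is measurable at baseline; it does not set the reference after SBRT. Raising it would change nothing for a 25 mm tumour that shrinks to 10 mm. Tying it to twice the slice thickness would mean up to 20 mm under the 10 mm cuts that 11.4 allows.
- The lack of a separate size rule for lymph nodes has little application. Patients are node negative at entry (Section 1), so a node should not be a baseline target.

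**Conclusion.** The point holds for the rule as written. Section 11.5.1 sets no absolute minimum, the reference is the running minimum, and one unconfirmed reading is an RFS event. The triggers of 1 mm at 5 mm, 2 mm at 10 mm, 3 mm at 15 mm and 4 mm at 20 mm are plain arithmetic. The false-progression rates are illustrative: about 1–42% (three readings) or 3–61% (four) for a 10 mm residual, and about 0–19% for 20 mm, under assumed residuals and a reading SD of 0.5 to 1.5 mm. They apply only to patients with such residuals and are not a forecast for the trial.

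A reader might infer that any difference of 1 to 2 mm will count as a relapse, or that the primary result will be invalid. The documents support neither: larger residuals need proportionally more growth, the governing text is unsettled, and the bias lowers observed RFS without raising type I error. This is a correctable weakness that should be fixed because the correction is cheap.

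**What to change.** In Section 11.5.1, define target progression as an increase of at least 20% over the smallest sum recorded on study **and** an absolute increase of at least 5 mm. State that this text governs RFS, LRC, TTLP and TTP. The 5 mm value is an assumption that is not found in the documents; the sponsor should confirm it. This also puts the reference value into the progression line itself, where it is now missing.

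No change to the measurable-lesion limit in 11.3 and no nodal rule is needed for this point.

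Cost: protocol wording and the measurement worksheet, with no extra scans. Downside: some true small regrowths will be called at the next scan, up to six months later. On a 10 mm residual the minimum amounts to 50% growth (5/10). A relapse called after the 24-month reading instead of at it would raise observed 2-year RFS, so the sponsor should weigh this when confirming the value.
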